7.3.6 Unscheduled visits

Unscheduled visits will be conducted if clinically required during the trial. During unscheduled visits, relevant clinical test, laboratory test, concurrent medication and AE data will be collected from the original medical records and CRFs if necessary.

7.3.7 Schedule of Events Table

Table 4 Schedule of Events Table

Study Period/Visits	Screening Period	Baseline Period	Study Period (5 days)		Safety Follow-up Period (D6-28)		Premature Withdrawal ¹⁸
Study Day (s)	D-14~2	D-1	D1	D2~D5	D6±1d	D28±2d	
Informed consent	x						
Inclusion/exclusion criteria	x	x					

Study Period/Visits	Screening Period	Baseline Period	Study Period (5 days)		Safety Follow-up Period (D6-28)		Premature Withdrawal ¹⁸
Study Day (s)	D-14~2	D-1	D1	D2~D5	D6±1d	D28±2d	
Demographics	x						
Physical examination	x			x			
Vital signs ¹	x		x	x			x
Medical history:	Personal history	x					
	Past history	x					
	Allergy history	x					
	Tumor History	x					
Tumor stage	x						
Pathological examination ²	x						
Laboratory examination ³	Blood routine	x			x		x
	Blood Biochemistry	x			x		x
	Electrolyte	x			x		x
	Thyroid Function	x					
	Coagulation Function	x			x		x
	Urinalysis	x					
	Blood Pregnancy (If Needed)	x					
	Serum Virology	x					
12-lead ECG	x				x		x
Cardiac function score	x						
Physical condition score	x						
Chest X-ray (can be ignored if there is chest CT) ⁴	x						
CT/MRI/PET-CT ⁵	x						
Administration							
[⁶⁸ Ga]Ga-NOTA-SNA002 administration ⁶			x				
Biological Samples, Imaging, Safety Data, Specimen Collection							
Blood sampling ⁷			x				
Urine sampling ⁸			x				
Ada ⁹			x		x	x	x
Pet-ct ¹⁰			x				
Measurement of radiation dose ¹¹			x				
Formulate a Plan for Obtaining Target Lesion Specimens (If Performed) ¹²			x				
Collection of tissue samples from target lesions (if performed) ¹³				x			
Pd-111 immunohistochemical examination ¹⁴	x			x			
Other							
Examination of injection site ¹⁵			x	x			
Enrollment ¹⁶		x					
Out of group						x	
Concomitant medications ¹⁷	x	x	x	x	x		x

Study Period/Visits	Screening Period	Baseline Period	Study Period (5 days)		Safety Follow-up Period (D6-28)		Premature Withdrawal ¹⁸
Study Day (s)	D-14~2	D-1	D1	D2~D5	D6±1d	D28±2d	
Ac ¹⁸			x	x		x	x
Distribute/recycle journal cards						x	

1. Vital Signs: tested during the screening period, 6 ± 1 hours after D1 administration, and 6 ± 2 hours after D2 biopsy (if performed).
2. Pathological Examination: if the pathological examination results within one year before screening are obtained, and the subject receives biopsy samples within two weeks before enrollment and has not undergone chemotherapy, radiotherapy, or immunotherapy until enrollment, biopsy may not be performed after administration in this clinical trial.
3. Laboratory examination: Subjects should obtain blood routine (red blood cell count, white blood cell count, hemoglobin, platelet count, neutrophil count, lymphocyte count, monocyte count), blood biochemistry (total protein, albumin, total bilirubin, alanine aminotransferase, aspartate aminotransferase alkaline phosphatase, glucose, creatinine, blood urea nitrogen), electrolyte (potassium, sodium, calcium), thyroid function (thyroid function, triiodothyronine, thyroxine), coagulation function (prothrombin time, thrombin time, fibrinogen), urine routine (bacterial count, glucose, red blood cells, white blood cells), serum virological (hepatitis B virus surface antigen, hepatitis C virus antibody, syphilis specific antibody, human immunodeficiency virus antibody). During the safe follow-up period D6, retest blood routine, blood biochemistry, electrolytes, and coagulation series (note: serum virology can accept results within 28 days before screening, while other laboratory tests can accept results within 7 days before screening).
4. Chest X-Ray: if there is chest CT, it can be ignored.
5. CT/MRI/PET-CT: imaging within one month prior to screening can be acceptable at the research center or other tertiary hospitals.
6. [⁶⁸Ga]Ga-NOTA-SNA002 Administration: slowly inject [⁶⁸Ga] Ga-NOTA-SNA002 intravenously on D1 for at least 1 minute. Before injection, the subjects should drink sufficient water to ensure proper hydration, and the amount of water consumed should not be less than 500mL. After administration, regular drinking and excretion should be carried out to reduce radiation exposure.
7. Blood Sampling: collected within 30 minutes before administration, 2 minutes (± 1 minute), 5 minutes (± 1 minute), 10 minutes (± 1 minute), 30 minutes (± 2 minute), 50 minutes (± 5 minute), 100 minutes (± 5 minute), and 150 minutes (± 10 minute) after administration. Each blood sample should be tested for whole blood radiation dose within 30 minutes after collection, and centrifuged within 10 minutes after measuring whole blood radiation dose. Serum radiation dose should be tested within 5 minutes after centrifugation. After testing, the separated serum samples are divided into cryopreservation tubes, frozen (-60 °C~90 °C), and regularly sent to the central laboratory for SNA002 protein content determination.
8. Urine will be pooled for renal radiotracer clearance before drug administration, 90±30 minutes, 180±30 minutes and 300±30 minutes post injection.
9. ADA: blood samples were collected within 30 minutes before administration, on D6 ± 1d and D28 ± 2d during the safe follow-up period. All blood samples were tested in an independent third-party central laboratory.
10. Systemic PET-CT: Three systemic PET CT scans are performed at 15±5 minutes, 60±10 minutes, and 120±20 minutes after administration. Panoramic PET-CT scans performed after dosing were acceptable for 1 to 2 subjects in a dose group or each dose group and were required to cover at least one of these time points.
11. Measurement of Radiation Dose: measure the surrounding radiation dose at 4 ± 0.5 hours after administration.
12. PD-L1 Immunohistochemical Examination and Formulate a Plan for Obtaining Target Lesion Specimens (If Performed) : Obtain the PD-L1 immunohistochemical results of the subjects at the study site during the screening period. This experiment determines whether to collect tissue specimens after administration based

on specific circumstances. If the subject has obtained a biopsy specimen within 2 weeks before enrollment and has not undergone any treatment, there is no need to perform another biopsy, otherwise the specimen needs to be collected again. Researchers need to determine the method of specimen collection based on the subject's situation, and can accept surgical resection of tumor tissue or biopsy for sampling. Surgical resection can be performed after 1 day of drug administration (i.e. after D2, surgical resection is generally performed between D2 and D5). Immunotherapy, chemotherapy, or radiation therapy should not be performed on the primary tumor disease during the period from drug administration to surgery. Biopsy sampling can include endoscopic (such as gastroscopy, fiberoptic bronchoscopy, laparoscopy, etc.) sampling and puncture biopsy sampling, generally conducted in D2. The preferred specimen for collection is the primary tumor tissue or metastatic lesion with the highest SUVmax. The collection principle is to collect at least one biopsy sample from the target tumor lesions that can be collected, and the maximum number of samples for the same patient should not exceed 5. Ideally, biopsies should be performed separately for positive and negative lesions under PET imaging in the same patient. The location of specimen collection and the selected collection method are determined by the researcher based on previous imaging results and PET results of this experiment. After obtaining target tissue samples, PD-L1 immunohistochemistry was performed at the research center.

13. Collection of Tissue Samples from Target Lesions (If Performed) :Specimens collected according to established target lesion specimen acquisition protocol from D2 to D5.
14. Examination of Injection Site: observe injection site for redness, swelling, heat, pain, itching and other symptoms 6 ± 1 h and 24 ± 6 h after administration.
15. Enrollment: The subjects were enrolled after reviewing the inclusion and exclusion criteria on D-1 again, and were hospitalized in the department of primary tumor due to primary tumor before D-1 and after D1. After the end of the trial period of this clinical trial, the possible continued hospitalization of the subjects was not affected.(Note: Researchers can arrange for subjects to enter a safe follow-up period based on their condition, after completing the collection of tissue specimens (D2) or surgical specimens (D2-D5) during the trial period, or after completing various operations in D1 for subjects who do not need to collect new tissue specimens, to shorten the waiting time for subsequent treatment from an ethical perspective.)
16. Concomitant Medications: Starting from the signing of the informed consent form, record the daily concomitant medication until the end of the trial. (For subjects who are no longer hospitalized, the safe follow-up period will be recorded in the diary card; if they continue to be hospitalized, the combination medication will be reflected in the hospitalization doctor's order, and drugs taken on their own or for underlying diseases for a long time can be recorded in the diary card).
17. AE: Record any AE observed by the subjects after administration until the end of the experiment. (For subjects who are no longer hospitalized, the safe follow-up period shall be recorded in the diary card; if hospitalization continues, adverse events shall be recorded in the hospitalization medical record).
18. Premature Withdrawal: For subjects who withdraw prematurely, laboratory tests such as vital signs, 12-lead ECG, blood routine, blood biochemistry, coagulation and electrolytes should be performed (if the subject withdraws after D6, and laboratory tests and 12-lead ECG have been performed on D6, they can no longer be performed), anti-SNA002 anti-drug antibody tests should be performed, and adverse events and concomitant medications of the subjects should be recorded.

7.4 Justification for Sensitive Procedures

Not applicable.

7.5 Precautionary Medications, Treatments, and Procedures

Prophylactic medications such as antihistamines (diphenhydramine or similar drugs) and antipyretics (acetaminophen or similar drugs) are permitted within 30–60 min prior to intravenous injection of SNA002.

For subjects who require glucocorticoid therapy for immune-related AEs, high-dose systemic glucocorticoids should be avoided, such as a single dose of > 200 mg hydrocortisone or > 50 mg

prednisone.

7.6 Prohibited Medications, Treatments, and Procedures

Except for the investigational drug, all systemic immunotherapies (e.g., Anti-PD-1/PD-L1 drugs or immunoreceptor inhibitors) are prohibited during the trial. If such therapies are used, the subject must withdraw from the study and the investigator will evaluate the impact of the concomitant medication on the investigational drug.

Immunostimulatory Chinese herbal medicines (e.g., mistletoe extract) or those known to interfere with important organ functions (e.g., hypericin) are prohibited during the trial.

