6.1.9 Duration of Therapy

Patients will be administered a single dose of SNA002. The duration of study participation will be approximately 42 days, including a screening period up to 14 days and a follow-up period up to 28 days (patients who experience AEs will be followed until resolution).

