8) Develop a plan for obtaining target lesion specimens (if applicable): Determine whether to collect tissue specimens after administration based on specific circumstances. If the subject has obtained a biopsy specimen within 2 weeks prior to enrollment and has obtained/can undergo immunohistochemical PD-L1 detection results (such as PD-L1 immunohistochemical detection of pathological tissues in different directions of the lesion collected through bronchoscopy within 2 weeks prior to enrollment), and no treatment has been given, no further biopsy is required. Otherwise, pathological specimens need to be collected in this clinical study. The collection method can accept biopsy or surgical resection of specimens, which is determined by the investigators based on the subject's situation.
 (note: the investigators can arrange for the subjects to enter a safe follow-up period after the subjects complete the tissue specimen collection (D2) or surgical specimen collection (D2-D5) during the trial period, or after the subjects who do not need to collect tissue specimens again complete all operations in D1, in order to shorten the waiting time for subsequent treatment from an ethical perspective).

9) Vital signs: Vital signs are evaluated at 6 ± 1 h after administration on D1.

10) Examination of injection site: observe injection site for redness, swelling, heat, pain, itching and other symptoms 6 ± 1 h after administration.

11) Record concomitant medications.

12) Record AEs.

D2 to D5

- 1) Target lesion specimen acquisition: Biopsy specimens can include endoscopic (such as gastroscopy, fiberoptic bronchoscopy, laparoscopy, etc.) and puncture biopsy specimens, which are generally conducted in D2. The preferred specimen for collection is the primary tumor lesion or metastatic lesion with the highest SUVmax; The collection principle is to collect at least one biopsy sample from the target tumor lesions that can be collected, and the maximum number of samples for the same patient is 5. Ideally, biopsies should be performed on both positive and negative lesions of the same patient under PET imaging. The location of specimen collection and the selected collection method will be determined by the investigators based on previous imaging results and the PET results of this experiment. Perform PD-L1 immunohistochemical detection after obtaining target tissue samples.

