- 2) If surgical resection is performed, it can be performed on the D2 to D5. Immunotherapy, chemotherapy, or radiation therapy should not be performed on the primary tumor disease during the injection of experimental drugs until the surgery period.
- 3) Vital signs: Vital signs are evaluated at 6 ± 2 h after paracentesis (if performed).
- 4) Physical examination: evaluated at 6 ± 2 h after biopsy (if performed).
- 5) PD-L1 IHC examination: The collected specimens will be sent to the pathology department to make pathological sections as required, and immediately sent by the cold chain transportation company (Shanghai Shengsheng Logistics Co., Ltd.) to an independent third-party central pathology laboratory (Beijing Geenga Medical Laboratory Co., Ltd.) for PD-L1 immunohistochemical examination. The requirements for specimen preparation transported to the central pathology laboratory can be found in the manual of the central pathology laboratory.
- 6) Examination of injection site: observe injection site for redness, swelling, heat, pain, itching and other symptoms 24 ± 6 h after administration on D1.
- 7) Record concomitant medications.
- 8) Record AEs.

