7.3.4 Safety Follow-up Period

D6 to D28

- 1) Anti-SNA002 antibody: Blood samples are collected on $D6 \pm 1$ d, $D28 \pm 2$ d and sent to the central laboratory for detection.
- 2) Laboratory examination: blood routine, blood biochemistry, coagulation, and electrolyte tests were conducted on $D6 \pm 1$ d.

- 3) 12-lead ECG: detected on D6 ± 1d.
- 4) Distribute diary cards during the safe follow-up period of D6 ± 1 days (if the subjects discharge immediately after biopsy, the diary cards will be distributed on the day of discharge; if the subjects are not hospitalized, the diary cards will be issued after completing the D1 examination), and collect the diary card on D28 ± 2 days.
- 5) Record AEs: all adverse events should be recorded in the diary cards (if the subjects continue to be hospitalized, adverse events will be recorded in the hospitalization medical record).
- 6) Record concomitant medications: all concomitant medications should be recorded in the diary card (if the subjects continue to be hospitalized, concomitant medications related to primary tumor treatment can be recorded in the hospitalization doctor's order, and medications taken on their own or for long-term underlying diseases can be recorded in the diary cards).
- 7) Trial completion: the study will be completion for subject after the relevant procedures on D28 ± 2d. Subject should be permitted to undergo relevant chemotherapy, radiotherapy and/or immunotherapy for the primary disease during the safe follow-up period.

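### Section 7.6 requires withdrawal for any systemic immunotherapy during the trial, but 7.3.4 permits immunotherapy in a safety follow-up that belongs to the trial until D28±2d

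*Combined protocol and SAP*

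**What the plan says.** Section 7.6 prohibits all systemic immunotherapies for the trial, naming anti-PD-1/PD-L1 drugs as an example. On use it states: "If such therapies are used, the subject must withdraw from the study". It gives no end date, makes no exception for follow-up and does not refer to 7.3.4.

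Section 7.3.4, item 7, covering D6 to D28, says: "Subject should be permitted to undergo relevant chemotherapy, radiotherapy and/or immunotherapy for the primary disease during the safe follow-up period".

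The follow-up belongs to the study:
- The Study Design part of the Protocol Summary lists it as one of four study periods.
- Section 6.1.9 gives a participation time of about 42 days, "including a screening period up to 14 days and a follow-up period up to 28 days".
- Section 7.3.4 says "the study will be completion for subject after the relevant procedures on D28" ±2d.
- Note 16 to Table 4 (7.3.7) tells sites to "record the daily concomitant medication until the end of the trial", then explains how to do so in the safety follow-up.
- Note 17 handles adverse events the same way: "Record any AE observed by the subjects after administration until the end of the experiment".

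A narrower restriction stands in 7.3.3, in the item on resection: "Immunotherapy, chemotherapy, or radiation therapy should not be performed on the primary tumor disease during the injection of experimental drugs until the surgery period". Section 7.3.3 also lets investigators move subjects into follow-up early, "in order to shorten the waiting time for subsequent treatment from an ethical perspective". Notes 12 and 15 to Table 4 repeat these two provisions.

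**The concern.** A site that follows 7.3.4 breaches 7.6, which 14.3 would class as a protocol deviation. A site that applies 7.6 as written withdraws a subject for treatment that 7.3.4 allows. Two sites, or two monitors, could handle the same subject differently.

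Two endpoints in 4.2 are touched: ADA incidence (secondary) and the incidence of TEAEs and SAEs (primary). Under a literal 7.6, subjects who start immunotherapy could have shorter ADA observation, and a shorter window for non-serious events, than subjects who do not. The difference would follow treatment choice and would not be random. Section 10.5 plans 3 to 7 subjects per dose level, so one such subject is 1/7 = 14% to 1/3 = 33% of a level.

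**Working it through.** **1. Is follow-up inside the trial?** The stated participation time reproduces only if follow-up is counted: 14 days of screening + 28 days of follow-up = 42 days.

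**2. How long do the two rules overlap?** D6 to D28 is 28 − 6 + 1 = 23 of the 28 days from D1, or 82%. A subject who needs no new tissue may enter follow-up once the D1 procedures are done. For that subject the overlap is D2 to D28, 27 of 28 days, or 96%.

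**3. Do the two rules cover the same treatment?** Section 7.6 speaks of systemic immunotherapies and 7.3.4 of immunotherapy for the primary disease. Anti-PD-1/PD-L1 treatment would ordinarily fall under both. Section 7.6 does not ban chemotherapy, radiotherapy or surgery, so the conflict concerns immunotherapy only.

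**4. What could a literal withdrawal cost?** The documents give no withdrawal days, so the days w below are assumed for illustration. A second assumption is that the early-termination ADA sample in 7.3.5 is drawn on day w; that section sets no timing. A third is that no later observations are made, although 5.3.2 asks for them. The figures are therefore the unfavourable end.

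Formulas, with dosing on D1:
- Last ADA sample, days after dosing: w − 1, against 28 − 1 = 27 planned.
- Non-serious AE collection under 8.3 (7 days past participation): ends on day w + 7; shortfall to D28 = 28 − (w + 7).
- SAE collection under 8.3 (30 days past participation): ends on day w + 30.

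| Assumed withdrawal | Last ADA, days after dosing (share of 27) | Non-serious AE collection ends (shortfall to D28) | SAE collection ends |
|---|---|---|---|
| D2 | 1 (4%) | D9 (19 days) | D32 |
| D6 | 5 (19%) | D13 (15 days) | D36 |
| D14 | 13 (48%) | D21 (7 days) | D44 |
| D21 | 20 (74%) | D28 (0 days) | D51 |

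SAE collection under 8.3 passes even the latest D28 visit (D30) in every row. The subject would have 1, 1, 2 and 2 post-dose ADA samples respectively, against 2 planned, and would stay in the denominator if any post-dose sample counts.

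Sections 8.4.1 and 8.4.2 give a narrower collection window that ends at the last follow-up. They still require follow-up of events within one month afterwards that cannot be judged unrelated to the drug.

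**The case against.** The strongest reply is that the intended meaning can be inferred. Sections 7.3.3 and 7.3.7 sometimes use a narrower trial period, before follow-up, and Table 4 labels D1 to D5 as a five-day study period. The treatment restriction in 7.3.3 ends at surgery, and early entry to follow-up exists so that therapy is not delayed. The rest of the withdrawal sentence in 7.6 asks the investigator to assess the effect of the other drug on the study agent, which suggests a concern about interference with a single D1 dose. A site could read 7.6 as covering D1 to D5 and 7.3.4 as the specific rule afterwards.

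The point about intent stands. It does not remove the conflict: 7.6 refers to the trial, not the trial period; its remedy is withdrawal from the study; and Table 4 note 16 uses the trial to include follow-up.

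The objection to data loss also has force. Section 5.3.2 asks that observations be completed whatever the reason for withdrawal. Section 5.5 stops data collection only when consent is withdrawn, and a 7.6 withdrawal is not that. Section 7.3.5 provides ADA, adverse event and medication records at early termination.

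A reader might go further and infer that these subjects' late safety and ADA data are lost, or that dose decisions are compromised. The documents do not support either. Observation may be shortened but is not stopped. The escalation rules in 6.1.7.2 count adverse reactions, and the termination rule in 5.4 and the halting rule in 8.5 count drug-related events. With no hypothesis test planned (10.2), no error rate or power is affected.

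**Conclusion.** The inconsistency is real and minor. Sections 7.6 and 7.3.4 give opposite instructions for immunotherapy in a follow-up that other sections count as part of the study, and nothing limits 7.6 to the time before it. Confidence is high for that textual conflict only.

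The consequence depends on a site applying 7.6 literally. In that case ADA observation and non-serious adverse event collection could be shortened for subjects who start permitted treatment. The loss is partial, and its size cannot be computed: the number of subjects, the day they start therapy, the day of the termination sample and site practice are all unknown. The day counts above show only what the rules would allow on assumed withdrawal days; they do not forecast what will happen. This is a drafting inconsistency, not a disputable design choice.

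**What to change.** In 7.6, limit the systemic immunotherapy ban and its withdrawal rule to the time until entry to the safety follow-up. Define that entry as completion of the D1 procedures or, where tissue is taken, completion of biopsy or surgery on D2 to D5. The last PET scan (120±20 minutes) would be too early an end point, because 7.3.3 schedules blood at 150 minutes and urine at 300 minutes.

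Add one sentence: subjects who start anticancer therapy under 7.3.4 remain on study for the D6 and D28 ADA samples, the D6 laboratory tests and ECG, and adverse event collection to D28±2d.

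The cost is two sentences and the IRB review that 13.2 requires for an amendment. No new eCRF field is needed. The downside is that late adverse events and the D28 ADA result in these subjects are observed under new therapy. The concomitant-medication record and the relatedness grading in 8.2.2 can take account of that.
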